2.1 – Our primary hypothesis is that, after reaching bilirubin levels > 2 mg/dL, patients receiving Omegaven® will reach a bilirubin level ≤ 2 mg/dL faster than patients receiving conventional fat emulsions. Additionally, while patients receiving Omegaven™ will experience a decrease in their levels of bilirubin and other hepatic enzymes over time, patients receiving conventional emulsions will maintain high levels of bilirubin and other hepatic enzymes over time.

2.2 – Patients with surgical gastrointestinal disease and cholestasis will have better clinical hepatic outcomes than patients receiving conventional emulsions.

2.3 – Since patients receiving Omegaven® will have improved immune function, they will have a lower infection rate than patients receiving conventional fat emulsions.

2.4 – Due to a better general hepatic condition, patients receiving Omegaven® will also experience lower occurrence of liver transplant, death from hepatic associated causes, and blood transfusions.

2. Background and Significance

Parenteral Nutrition Associated Liver Disease (PNALD)

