- a) The patient will be PN dependent and at risk for significant hepatic injury due to prolonged use of parenteral nutrition.
- b) Have significant hepatic dysfunction due to parenteral nutrition despite utilization of all conventional therapies.

Inclusion Criteria:

1. Patients will be PN dependent (unable to meet nutritional needs solely by enteral nutrition) and are expected to require PN for at least another 30 days
2. Patients considered eligible for study participation must have parenteral nutrition associated liver disease (PNALD) as defined as a direct bilirubin of ≥ 2 mg/dl or currently on Omegaven through another protocol. Other causes of liver disease should be excluded. A liver biopsy is not necessary for treatment.
3. Direct bilirubin > 2.0 mg/dl, or already on Omegaven through another protocol.
4. Signed patient informed consent.
5. The patient must have utilized standard therapies to prevent the progression of his/her liver disease including surgical treatment, cyclic PN, avoiding overfeeding, reduction/removal of copper and manganese from PN, advancement of enteral feeding, and the use of ursodiol (i.e., Actigall[®]).

Exclusion Criteria:

1. Pregnancy
2. Other causes of chronic liver disease (Hepatitis C, biliary atresia, and alpha 1 anti-trypsin deficiency,)
3. Enrollment in any other clinical trial involving an investigational agent (unless approved by the designated physicians on the multidisciplinary team)
4. The parent or guardian or child unwilling to provide consent or assent

In rare instances, patients diagnosed with PNALD may later be found to have liver disease due to other causes in addition to the use of PN (i.e., inborn errors of metabolism, viral infections). Such causes may not be known at the time of enrollment and will not preclude them from continuing in the study. For the sake of statistical analysis, however, these patients will be excluded although all data will be collected and reviewed.

Screening Procedures

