Because both Intralipid® and Liposyn® II are isotonic, both could be infused through either a central or peripheral line. Both products are compatible with parenteral nutrition solutions and were co-infused via y-site. Source container hang times varied during this period, and IFE was either infused from a single container over 24 hours or the container was changed every 12 hours per CDC recommendations. Also during this period, the administration method of PN changed. Prior to 1999, standard 0.2 micron inline filters were used routinely and only PN but not IFE could be infused through them (IFE was infused via y-site beneath the filter). After 1999, 1.2 micron filters became the standard inline filter, allowing for IFE to be filtered along with the PN solution.

Duration of Therapy

Patients remained on either Liposyn® II or Intralipid® until weaned from PN.

Discontinuation of Therapy

Patients at risk for malnutrition or resumption of PN were typically followed by the Clinical Nutrition Service for several months following discontinuation of PN.

ADDITIONAL PREDICTORS OF INTEREST

Since decisions about starting Omegaven® administration will follow a compassionate protocol, we expect that patients receiving Omegaven® will present more severe liver disease than the controls from the historical cohort. Therefore, to correct confounding biases, we anticipate the need to adjust for potential predictors of liver outcomes at baseline. Baseline will be defined as: the date that treatment starts for Omegaven® patients and on the date that patient reached bilirubin levels > 2 for soybean based fat emulsion patients.

The following predictors of liver disease will be considered:

- Baseline direct bilirubin levels.
- Diagnosis of Necrotizing Enterocolitis (vs. any other disease)
- Gender (male vs. female)
- Age (≥ 8 months vs. < 8 months)
- Gestational age
- Birth weight
- Race

To assess patients comparability, we will also descriptively explore trends in direct bilirubin level before the beginning of follow-up (start of treatment date for Omegaven® patients and date in which direct bilirubin level raised to > 2 mg/dL for control patients)

Subgroup Analysis

With exploratory purposes, we will describe safety and/or efficacy of Omegaven® in subgroups of patients including younger (vs. older) patients at baseline, patients who presented with infections (vs. who did not),

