Analysis of Baseline Characteristics

For statistical purposes, baseline values will be defined as the last measurement before starting to administer Omegaven® for patients, in the treatment group, and as the measurement taken when a patient first had a direct bilirubin level > 2 mg/dL recorded, in the historical control group. Descriptive statistics for all baseline relevant risk factors will be summarized for Omegaven® (omega-3 based fat emulsion) and historical control (soybean oil fat emulsion) groups. Associations between categorical predictors and Omegaven® vs. soybean oil fat emulsion groups will be tested through chi-square tests. Associations between continuous predictors and treatment groups will be studied through means (and standard deviations) and t-tests, or medians (and interquartile ranges) and Wilcoxon tests, when appropriate.

Analysis of Safety and Tolerability of Omegaven®

All primary safety and tolerability analyses will be based on descriptive statistics. In secondary analyses, we will also assess the statistical significance of differences. Some safety and tolerability outcomes will be measured only in the Omegaven® group. For those, we will compare results before starting PN with Omegaven® (while receiving PN with soybean oil fat emulsions) with after starting PN with Omegaven®. The period receiving Omegaven® will start to be counted 30 days after beginning PN with Omegaven® for the main analysis. Outcomes measured in the Omegaven® and soybean oil fat emulsion groups will be described separately for each of those groups for a period starting 30 days after baseline, i.e., 30 days after starting PN with Omegaven®, for the treatment group, and 30 days after bilirubin > 2 mg/dL, for the soybean oil fat emulsion group.

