We will also describe individual profiles over time (i.e., 2 months before baseline or birth until end of follow-up period) for all subjects using graphical methods. Trends in liver function markers over time will be explored using generalized linear models in which correlations of observations within subjects will be accounted using a generalized equations or random effects approach. In these models we will hypothesize that for both groups biochemical levels increase for all tests with equal slope before treatment. After treatment, however, levels should be decreasing for patients in the Omegaven® group. We will perform these analyses including only subjects who did not die or undergo transplantation and including all subjects but assigning for subjects who died or underwent a transplant their worse possible outcome after they died or had the transplant. Using descriptive statistics, we will also explore the association between spikes in blood tests over time and predictors including transfusions of red blood cell products and blood stream infections.

Assessment of efficacy will be also based on comparison of means (or medians) of the mean and maximum modified PELD scores of each subject across all follow-up weeks. Adjustments of these comparisons for potential confounders will be based on linear regression models. Mean rates of infection will be compared using logrank and Cox proportional hazards models. Proportions of liver transplant, mortality, and red blood cell product transfusion events between the two groups will be compared via Fisher's exact test (or Chi-square tests, when appropriate). Adjustments for potential confounders will be considered using exact stratified analysis and logistic regression models.

Missing Values

Since data will be prospectively collected in the Omegaven® group, we anticipate that data will be nearly complete, particularly for the safety outcomes. In both groups, we will explore imputing any laboratory values that are missing up to two visits in the middle of the follow-up period using linear or non-linear interpolation, as appropriate. To interpolate direct and total bilirubin, we will primarily use the two closest observations, since bilirubin could be very different in points in time located further apart from the missing observation. We will compare conclusions of analyses based on imputed values with analyses based on the available information.

Potential Study Limitations

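### The exploratory liver-marker models are framed with equal pre-treatment slopes although time zero differs by group; if that equality is imposed and is false, the post-baseline comparison can be biased in either direction

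*Combined protocol and SAP*

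**What the plan says.** Section 5c, Analysis of Efficacy of Omegaven, states: "Trends in liver function markers over time will be explored using generalized linear models", with GEE or random effects to handle within-subject correlation. Profiles are plotted from 2 months before baseline (or from birth) to the end of follow-up. On the shape of the models: "In these models we will hypothesize that for both groups biochemical levels increase for all tests with equal slope before treatment". After treatment, "levels should be decreasing for patients in the Omegaven® group". No model equation, between-group contrast or significance level is given for this analysis.

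Time zero is set in section 4d, Additional Predictors of Interest: "Baseline will be defined as: the date that treatment starts for Omegaven® patients and on the date that patient reached bilirubin levels > 2", the second rule being the one applied to controls. Section 5c, Analysis of Baseline Characteristics, is more specific about the control value: "as the measurement taken when a patient first had a direct bilirubin level > 2 mg/dL recorded, in the historical control group".

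The models bear on the second part of hypothesis 2.1, that markers fall on Omegaven while "patients receiving conventional emulsions will maintain high levels of bilirubin and other hepatic enzymes over time". Section 4d also plans a descriptive look at direct bilirubin trends before follow-up begins.

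**The concern.** The two time zeros are different clinical events. A control enters at the first recorded crossing of 2 mg/dL, so every earlier recorded direct bilirubin for that child is at or below 2 and the pre-baseline rise is shaped by that selection. An Omegaven patient enters at treatment start. By then bilirubin is normally already raised, and an inclusion criterion reads: "The patient must have utilized standard therapies to prevent the progression of his/her liver disease". The period before treatment may be a plateau or a steep rise. The selection argument applies directly only to direct bilirubin, but the equal-slope statement covers every test.

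If an analyst turns the sentence into a single pre-baseline slope shared by both groups, the model cannot fit both pre-baseline periods. The fitted level at baseline shifts, and the post-baseline slope tilts to compensate. A plateau before treatment would then create an apparent Omegaven benefit, and a steep rise before treatment would hide a real one. At stake is the supporting claim that markers fall on Omegaven and stay high on soybean emulsion.

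**Working it through.** The plan gives no power, error rate or alpha for these models, so there is no figure to reproduce. The check has three steps.

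**Inputs.** From the documents: a 2-month pre-baseline window (5c, efficacy); control data at two-week intervals (4f); 25 per group, the middle of the 20, 25 and 30 in the safety power tables (5d). Assumed: two-sided 5% level; control pre-slope about 0.7 mg/dL/month; Omegaven pre-slope from 0 to 2.0; Omegaven baseline mean 6 mg/dL; residual SD 0.5 mg/dL; slope SD 0.3; follow-up of 3, 6 or 12 months.

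**Step 1: how much misfit is passed on.** The constrained model has a separate level at baseline and a separate post-slope for each group, and one shared pre-slope. Let t be months from baseline, u = min(t, 0) and v = max(t, 0), with visits every half month. With equal group sizes and exchangeable correlation, the bias in the post-slope difference (Omegaven minus control) is

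bias = k × (Omegaven pre-slope − control pre-slope), where k = Σ|u| × Σv / (N × Σv² − (Σv)²).

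The pre-baseline visits at −2, −1.5, −1 and −0.5 give Σ|u| = 5.

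- 3 months: N = 11, Σv = 10.5, Σv² = 22.75. k = 52.5 / (250.25 − 110.25) = 0.375.
- 6 months: N = 17, Σv = 39, Σv² = 162.5. k = 195 / (2762.5 − 1521) = 0.157.
- 12 months: N = 29, Σv = 150, Σv² = 1225. k = 750 / (35525 − 22500) = 0.058.

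At 3 months, against a control pre-slope of 0.7:

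- Omegaven pre-slope 0: 0.375 × (0 − 0.7) = −0.26 mg/dL/month, favouring Omegaven.
- Omegaven pre-slope 1.5: 0.375 × 0.8 = +0.30, against Omegaven.
- Omegaven pre-slope 2.0: 0.375 × 1.3 = +0.49, against Omegaven.

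Simulated biases were −0.29, +0.27 and +0.45. The factor k falls steeply as follow-up lengthens.

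**Step 2: false rejection.** GEE simulations used identical flat post-slopes in both groups and selected controls by first crossing. The ranges cover codings that differ in details the documents leave open, such as the spread of control baselines. At 300 replicates the Monte Carlo SE is at most √(0.25/300) = 2.9 points.

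| Omegaven pre-slope (mg/dL/month) | Shared pre-slope, 3 months | Shared pre-slope, 6 months |
|---|---|---|
| 0 | 84–98% | 30–38% |
| 0.35 | 40–67% | 12–19% |
| 0.7 | 6–23% | 5–8% |
| 1.5 | 51–83% | 17–25% |
| 2.0 | 97–100% | 51–64% |

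One further coding gave 10–49% across these pre-slopes at 6 months. At 12 months the range was 5–15%. With group-specific pre-slopes, rejection was 3–9%.

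**Step 3: is freeing the pre-slopes enough?** A second null gave both groups the same natural history on the log scale (rise 0.12 per week, residual SD 0.25, peak about 6 weeks after crossing), again with 25 per group and no drug effect.

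- Straight-line course, controls aligned at the exact crossing: 4–5% with a shared pre-slope, whatever the delay to treatment.
- Straight-line course, first recorded crossing: 13–15% with a shared pre-slope, nearly all against Omegaven; 5–6% with group-specific pre-slopes.
- Course that levels off or falls, with treatment 4 to 8 weeks after crossing: 4–63% with a shared pre-slope, but 91–100% with group-specific pre-slopes, all favouring Omegaven.

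In the last case the true post-baseline slopes differ because the groups are at different disease stages at time zero. An extra pre-slope term cannot correct that.

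**The case against.** The strongest reply is that the plan only explores these trends and only hypothesizes equal slopes. It states no constraint, post-baseline slope test or alpha. A reader might infer that the models force equal slopes and that the slope test therefore rejects without a drug effect. The documents do not support that: a constraint is one possible reading, and the error also depends on pre-slopes and follow-up lengths they do not give. Nor do different baselines by themselves make pre-slopes differ. Step 3 shows nominal error for a straight-line course with exact crossing; a bending course with a treatment delay, or selection at first crossing, is also needed.

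A reader might also infer that the efficacy conclusion is at risk, or that a fall within the Omegaven group is the planned test. Primary efficacy is time to bilirubin normalization, analysed separately by log-rank and Cox methods. The plan specifies no within-group test here, and hypothesis 2.1 is a between-group claim.

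The plan has partial safeguards: graphical checks of assumptions, individual profiles from before baseline, a descriptive look at pre-baseline bilirubin, baseline covariates, and a limitations section that names non-comparability. These reduce the risk of an unnoticed misfit. None says what happens to the model if the slopes differ, and the pre-baseline trend check covers direct bilirubin only. The limitations section expects the severity difference to weaken the apparent effect, whereas the working shows error in both directions.

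**Conclusion.** The point holds in conditional form. The equal-slope statement is unsupported given the two time zeros. If it is imposed and the pre-slopes differ, it can produce false differences in either direction. Under the assumed inputs the effect is large at about 3 months, moderate at 6 and near nominal by 12. The percentages show a range and are not estimates for this study, because pre-slopes, variability, treatment delay and follow-up length are all assumed.

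The consequence is limited to an exploratory analysis supporting the second part of hypothesis 2.1. A change is still worthwhile because the wording leaves an avoidable modelling error open and the correction is nearly free. Group-specific pre-slopes remove the bias from the constraint but leave confounding by disease stage, which can be the larger problem.

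**What to change.** Replace the equal-slope sentence in section 5c with wording to this effect:

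- Pre-baseline slopes are estimated separately by group (a group by pre-baseline time term) and reported for every marker as a check on comparability.
- The contrast is the group by post-baseline time interaction with its 95% CI, not a decrease within the Omegaven group alone.
- A sensitivity analysis aligns both groups at the first direct bilirubin above 2 mg/dL, with treatment start as a time-varying change point, for Omegaven patients whose earlier records exist.
- Results are labelled exploratory, with a statement that freeing the pre-slopes does not remove confounding by disease stage.

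The cost is SAP wording, extra model terms, slightly wider intervals and a little more analysis. The main model needs no new data, since values from 2 months before baseline are already used. The aligned analysis depends on earlier bilirubin records, which may be incomplete for patients referred from other facilities.

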The main limitation of our study results from the lack of comparability between the Omegaven® and historical control groups leading to potential confounding biases in our results. Two concerns could be: a) several health care standards and reporting systems changed (possibly improved) over the last 25 years (period in which controls were enrolled); and b) Omegaven® cases may be more severe, with more

advanced PNALD than historical controls, since they will be enrolled under a compassionate use protocol. Biases due to general improvement of health care outcomes could bias against controls the actual differences in safety (such as line infections) outcomes between Omegaven® (outcomes recorded now) and historical controls (outcomes recorded in the past). Conversely, improvement in reporting systems over time would tend to bias results in opposite direction, i.e., against Omegaven®. Since both biases may occur, we would expect that they would reduce or cancel each other. Also, we will compare all safety outcomes before and after treatment started in patients receiving Omegaven®, and compare conclusions of these analyses with analyses comparing Omegaven® with historical controls. Biases due to differential severity of omegaven and historical control patients is likely to occur but decrease the potential truth effect of Omegaven®.

Biases in our efficacy estimates could also result from misclassification, since our marker or reversal of cholestasis, i.e., direct bilirubin does not accurately translate all components of liver function. Also, and more importantly biases could result from missing data, since more missing data is expected to occur in historical controls than in the Omegaven® cohort (differential pattern of missing). Misclassification due to lack of specificity or sensitivity of direct bilirubin as a marker of cholestasis would likely to be random, and thus lead to underestimation of the true effect of Omegaven® in reversal of cholestasis. Biases due to more outcomes missing in the control than in the Omegaven® group could lead to an overestimation of the effect of Omegaven®.

d. Statistical Power and Sample Considerations

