The number of subjects included in the Omegaven® group will be based on a compassionate use protocol and not on study power considerations. The number of subjects included in the soybean oil fat emulsion historical cohort group will not be based on study power considerations but rather on the number of eligible subjects from a pre-existing cohort.

The primary safety analysis will be descriptive and not based on statistical significance. However, in Table 4 we outline power to detect several differences in the frequency of adverse events, assuming 20, 25, or 30 patients, diverse proportion of subjects with adverse event in either treatment period and not with the adverse event in the other (proportion of discordant pairs), for a two-sided 5% significance level McNemar's tests. Table 5 includes estimates of power for a Fisher's exact test when comparing Omegaven® with historical control groups, assuming diverse frequency of occurrence of the adverse event in the control group, equal number of subjects in each group, and diverse differences in proportions between Omegaven® and soybean oil fat emulsion groups.

For lower proportions of discordant pairs, we would generally attain close to 80% power in McNemar's test. Even for higher proportions of discordant pairs, assuming the high differences between before and after treatment that we expect to observe, e.g., 50% or more, 80% power can be attained in McNemar's test (Table 4). In Fisher's exact test, we will attain 80% power or more to detect differences between Omegaven® and historical controls of 45% or larger, regardless of the frequency of adverse events in each group (Table 5).

Table 4 – Power to detect varying differences in proportions before and after treatment with Omegaven® in a McNemar's test. All calculations were based on an alpha significance level of 0.05.

Difference between proportions	Proportion of discordant pairs	McNemar's Test		
		Sample size in the Omegaven™ group		
		20	25	30
30%	40%	59%	72%	81%
	60%	44%	55%	63%
50%	60%	92%	97%	99%
	80%	79%	88%	93%
80%	85%	>99%	>99%	>99%
	95%	>99%	>99%	>99%

*Calculations performed Statxact.

Table 5 – Power to detect varying differences in proportions between Omegaven® and historical control groups in a Fisher's exact test. All calculations were based on an alpha significance level of 0.05.

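### The regression adjustment of mean and maximum PELD does not name baseline PELD, so part of the expected severity gap may remain, biased against Omegaven

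*Combined protocol and SAP*

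**What the plan says.** Section 5c, Analysis of Efficacy of Omegaven, bases part of the efficacy assessment on a "comparison of means (or medians) of the mean and maximum modified PELD scores of each subject across all follow-up weeks". It continues: "Adjustments of these comparisons for potential confounders will be based on linear regression models".

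The covariates come from Additional Predictors of Interest (section d, study treatments and predictors). That section gives the reason for adjusting: "we expect that patients receiving Omegaven® will present more severe liver disease than the controls from the historical cohort", and so, "to correct confounding biases, we anticipate the need to adjust for potential predictors of liver outcomes at baseline". The predictors to be considered begin with "Baseline direct bilirubin levels". The others are necrotizing enterocolitis, gender, age, gestational age, birth weight and race. Baseline is "the date that treatment starts for Omegaven® patients and on the date that patient reached bilirubin levels > 2" for the soybean-oil patients.

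Potential Study Limitations adds: "Biases due to differential severity of omegaven and historical control patients is likely to occur but decrease the potential truth effect of Omegaven". It also says that direct bilirubin is an imperfect marker that misses some components of liver function.

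The text available for review does not name baseline PELD as a covariate or plan a change-from-baseline PELD analysis. By contrast, weight and height Z-scores are analysed as differences from baseline.

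**The concern.** A patient's mean or maximum score over follow-up depends on where that patient started. In a non-randomised comparison whose authors predict a severity imbalance, the starting level of the same score is the natural first covariate. Here it is replaced by one laboratory value that the plan itself calls incomplete.

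Because the Omegaven group is expected to start higher, any uncorrected part of the gap makes Omegaven look worse on PELD and can hide a benefit.

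The maximum is the more exposed of the two summaries. The plan does not say whether the baseline week is a follow-up week. If it is, a patient whose score falls from the first week onward is still scored at the starting value.

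**Working it through.** **Plan's own figure.** None. The documents give no standard deviation, effect size, correlation or power for PELD, so what follows is an illustration under stated assumptions.

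**Inputs.**
- From the plan: raw mean and maximum PELD; linear-regression adjustment; baseline direct bilirubin as the only listed severity covariate; Omegaven patients expected to be sicker.
- Assumed: rho, the within-group correlation of baseline with follow-up PELD; r, the within-group correlation of baseline bilirubin with baseline PELD; g, the baseline PELD gap in SD; a bilirubin gap of r × g SD; bilirubin related to follow-up PELD only through baseline PELD.

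**Bias carried into the comparison, in SD of follow-up PELD.**
- Crude: rho × g.
- Adjusted for bilirubin: the slope of follow-up PELD on bilirubin is rho × r, so rho × g − (rho × r)(r × g) = rho × g × (1 − r²) remains.
- Adjusted for baseline PELD: 0 under this model.

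The share left after bilirubin adjustment is 1 − r²: 1 − 0.25 = 75%, 1 − 0.49 = 51% and 1 − 0.81 = 19% for r = 0.5, 0.7 and 0.9. It does not depend on rho or g. With g = 0.5 SD:

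| rho | Crude | Bilirubin, r = 0.5 | r = 0.7 | r = 0.9 | Baseline PELD |
|---|---|---|---|---|---|
| 0.3 | 0.15 | 0.11 | 0.08 | 0.03 | 0 |
| 0.5 | 0.25 | 0.19 | 0.13 | 0.05 | 0 |
| 0.7 | 0.35 | 0.26 | 0.18 | 0.07 | 0 |
| 0.9 | 0.45 | 0.34 | 0.23 | 0.09 | 0 |

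The bilirubin gap matters. If it were g rather than r × g, the remaining share would be 1 − r: 50%, 30% or 10%.

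**Precision.** With n per group, the variance of the treatment estimate adjusted for baseline PELD, relative to the crude one, is (1 − rho²) × [1 + g² × n / (4(n − 1))]. The second factor is the price of an unequal baseline. The plan gives no PELD sample size; n = 25 is the middle value of its safety power tables.
- g = 0: 0.91, 0.75 and 0.51 for rho = 0.3, 0.5 and 0.7.
- g = 1: the bracket is 1 + 25/96 = 1.260, giving 0.91 × 1.260 = 1.15, 0.75 × 1.260 = 0.945 and 0.51 × 1.260 = 0.64.

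So with a large gap the precision gain is nearly gone at rho = 0.5 and is a loss at rho = 0.3.

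**Maximum.** If week 0 is included, the maximum is at least the week-0 score for every patient, so the group that starts higher has the higher floor. Dropping week 0 removes the floor but not the dependence of early weeks on the starting level. The covariate is still needed.

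**The case against.** The strongest reply is that the plan already deals with severity. It adjusts exactly these comparisons by linear regression, gives the expected imbalance as the reason, and lists baseline bilirubin first. It also says openly that severity bias would reduce the apparent effect of Omegaven. This stands. A reader might infer that the plan takes the whole starting gap for a treatment effect, but that describes only the crude comparison. The predictors are ones to be considered, so baseline PELD is unnamed rather than excluded.

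A reader might also expect baseline adjustment to bring a definite rise in power, say from 80% to 90% at a correlation of 0.5. That figure assumes balanced baselines and a model without bilirubin. The plan predicts imbalance and lists bilirubin, so neither condition fits.

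Three further points limit the concern. Modified PELD is not defined in the text available, so how much of it bilirubin represents cannot be read from the documents. The case rests instead on the plan's own remark about bilirubin, which it makes about bilirubin as an outcome marker; the remark applies equally to bilirubin as a covariate. Control data come from a spreadsheet abstracted at two-week intervals, with more missing values expected, so a baseline score may not exist for every control. And PELD is not the primary efficacy outcome, which is time to bilirubin normalization.

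None of this shows that bilirubin is enough. A control's baseline bilirubin is by definition the first recorded value above 2 mg/dL, so control values may cluster just above that limit, which would restrict what the adjustment can correct.

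**Conclusion.** The concern holds in a limited form. The PELD regression names no baseline PELD term, its listed severity covariate is a partial proxy by the plan's own account, and the plan predicts the imbalance that makes this matter. The adjusted comparison may therefore keep some of the starting gap. Under the model above, 75%, 51% or 19% of the carried-over gap remains at r = 0.5, 0.7 or 0.9; with g = 0.5 SD that is 0.03 to 0.34 SD across the values tabulated. These sizes rest on assumed correlations, an assumed gap and bilirubin acting only through PELD.

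The expected direction is against Omegaven: the omission would mask a benefit, not create one. The floor on the maximum is conditional on the baseline week being counted, which the plan leaves open. The documents support neither the reading that the full gap is taken as treatment effect nor any particular power gain. The change should be made, but the primary efficacy conclusion does not depend on it.

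**What to change.** In section 5c, Analysis of Efficacy:
- Include baseline modified PELD as a covariate in the linear models for mean and maximum PELD. It may replace baseline bilirubin there if the two are collinear.
- State that the adjusted estimate is the main PELD result and the crude comparison is descriptive.
- Compute each patient's mean and maximum from post-baseline weeks only.

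The cost is one covariate and a few sentences, with no new data collection where the inputs to a baseline score were recorded. Two things need to be written down. The plan must say how controls without those inputs are handled, for example by a stated window around baseline, with the number lacking a score reported. It should also acknowledge that baseline is treatment start in one group and the first bilirubin above 2 mg/dL in the other, so patients with equal baseline PELD may be at different stages of disease and some non-comparability will remain. No power figure should be attached to the change.
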